### Adverse Event Management

Adverse Events, Serious Adverse Events and Unanticipated Problems will be reported to members of DSMB by the PI immediately for independent review. These events will be managed by the PI, Co-PI, and Co-Investigators at the direction of the DSMB and UChicago Medicine Biological Sciences Division Institutional Review Board.

## XIII. Payment to subjects

Participants will not receive payment for participation.

## XIV. Procedures to obtain and record informed consent

Consent will be sought by our Clinical Research Coordinators over the phone using a virtual consent procedure (APPENDIX A). In the event a potential subject has difficulty with the virtual consent method, we will meet the subject in our research offices to sign the consent form in-person by providing them the RedCap eConsent form using an iPad. Since we are seeking healthy volunteers from the community, we do not believe any individual will require determination for capacity to consent.

After a potential subject expresses interest via email, in-person, or phone, potential subjects will complete the preliminary screening of self-reported underlying health conditions as described in the exclusion criteria via a screening phone call from the CRC/RA and consent will be sought virtually. In rare instances when subjects have difficulty signing the consent form virtually, the RedCap eConsent will be provided to them in-person by research staff using an iPad and they will sign and date digitally. Both subjects who sign the consent form virtually and in-person will receive a signed copy of the consent form to the email address provided at the start of the RedCap eConsent form. For those signing in-person, signed consents will be printed by request.

At the beginning of the consent process, subjects will be asked to verify their identity by emailing or texting the study email or study cell phone a photo of their diver's license, state ID, passport or employee ID. They will be asked for their email address where a signed copy of the consent form will be sent for their records. In the consent form, subjects will be informed about the nature of the intervention, that they will be receiving a daily dose of vitamin D, either low or moderate/high, and must self-administer this dose each day. They will be informed about the nature of the intervention, that they are blinded to the dose they receive. Subjects will be reminded that participation is entirely voluntary, and they may withdraw at any time without consequence. Subjects will also be informed about the data collection methods, including the survey and testing they will undergo at each stage, and that they will be informed about test results for COVID-19 antibodies only during the study period. They will be informed that their PTH, calcium and vitamin D results will be withheld until completion of study participation unless they suggest a safety concern. They will be educated about the risks of the study as described above in "Potential Risks". Subjects will be informed about what will be done if they are found to be hypercalcemic: First, they will be told to cease vitamin D supplementation. Subjects at UCM with a calcium level 10.5-12 mg/dL and at Rush with a calcium level 11.3-12mg/dL will be instructed to consult with their primary care physician. All subjects with a calcium level of 12.1-14 mg/dL will be referred to urgent care. All subjects with a calcium level greater than 14 mg/dL will be referred to the emergency room. These participants will continue to undergo monitoring blood draws and surveys and may resume vitamin D supplementation per study protocol with a physician note.

Subjects will then be instructed to select their randomization preference on the consent form. If a potential subject says they are already taking a supplement or supplements that contains 2,000IU or less of vitamin D in total, they may continue to take those supplements while part of the study, however, they will only be allowed to enroll in the arm that randomized them between 400 and 4,000IU.

If a potential subject says they are already taking a supplement or supplements that contains more than 2,000IU vitamin D in total, we will ask the subject to discontinue supplements in excess of 2,000IU during their time on the study supplement to keep the guidelines straightforward for participants and avoid any potential for overdose.

After consenting, subjects will be asked to visit the laboratory to obtain the initial blood test to screen for abnormal PTH and calcium levels, obtain baseline 25(OH) vitamin D levels, and determine the presence of COVID-19 antibodies. After the initial blood tests, to improve compliance with vitamin D supplementation and screen for patients who may only be interested in joining the study to obtain baseline labs / antibody levels, subjects will be called and offered the opportunity to withdraw from the study after initial lab results are available, prior to randomization. We will also tell subjects about their other lab results if they suggest a safety concern and are outside normal ranges outlined in the exclusion criteria. If potential subjects have declined to withdraw at this initial stage, we will proceed with randomization.

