### Dose, Frequency, and Administration of the Intervention

Subjects will receive one bottle of a 9-month supply of a vitamin D dose depending on the arm they are randomized to and contingent on their preference for moderate vs. high vitamin D dose. At the end of the study, subjects will be asked to discard any remaining pills in their bottle given that some subjects participate for 3-6 months of follow-up if recruited after October 1, 2022. A low-dose treatment arm (400 IU) will be compared with those in the moderate (4,000 IU/day) to high (10,000 IU/day) treatment arm. Subjects will retrieve blinded bottles containing a 9-month supply of vitamin D at the DCAM pharmacy if they live or work closer to UCM, and at the Rush University Professional Office building, [name] if they live or work closer to Rush. In the event subjects are unable to pick up their vitamin D bottles in these physical locations, bottles will be mailed to an address they provide. The source of the intervention will be the University of Chicago Investigational Drug Service where the bottles will be distributed to DCAM and [name]'s lab at Rush.

**1) Dosing.** The proposed trial will compare high dose (10,000 IU/d) or moderate dose (4,000 IU/d) to low dose (400 IU/d) vitamin D as opposed to lower doses, e.g., 2,000 IU/d maximum dose in the Harvard trial. Schwartz et al. (left panel below) show that 800 or 2000 IU/d produce average levels of only about 35 ng/ml compared to 40-45 ng/ml for 4000 IU/d and 55 ng/ml for 50,000 IU/week. Data from McCullough et al. (Panel A, B below) shows that long-term administration of 10,000 IU/d produces much higher steady state vitamin D levels (about 95 ng/ml) compared to 5000 IU/d, producing about 60 ng/ml. Given the data discussed above on uncertainty about the optimal vitamin D intake/levels for immune function, this innovation in our proposed trial is potentially highly significant.

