8. Report already taking more than 400 IU of vitamin D daily as recommended by their health care provider, excluding multivitamins and excluding supplements that include vitamin D and calcium together, unless permission is received from the prescribing health care provider to participate. In this case, no more than 1,000 IU vitamin D may be taken daily in addition to the study medication and we would limit the subjects to participation in the low vs. moderate arm of the study, producing a maximum dose of 5,000 IU per day. We note that the NAM recommended a maximum dose of 4,000 IU per day without medical supervision based on evidence that 5,000 was safe and known uncertainty about the precision of dosing in 5,000 IU supplements available over the counter. However, since we are testing the dosage of our 4,000 IU supplements to high precision and these patients would be taking their original supplements with a labelled dose of 1,000 IU or less, we think that the combination of our 4,000 IU supplements and the patient's original supplement of up to 1,000 IU should not provide a maximum dose meaningfully above the 5,000 IU actual dose the NAM has considered safe for taking without medical supervision. We note further that we are measuring vitamin D levels and PTH in these patients regardless in this study. We do, however, have another study of vitamin D and COVID (IRB# 20-0847), in which we are not measuring these levels, for which it is more important to not substantially exceed NAM maximum level of 5,000 IU per day. The approach described here allows us to align the approach in these two studies.
9. Report taking D2.
10. Report a history of sarcoidosis.

11. Screen positive for hypercalcemia ( at UCM, defined as >10.4 mg/dL and at Rush, defined as >11.2 mg/dL) during the initial blood test.
12. Screen positive for hyperparathyroidism (PTH>85 pg/dL) during the initial blood test with calcium  $\geq 10$ mg/dL and normal levels of vitamin D ( $\geq 30$ ng/mL)
13. Have vitamin D levels of >100ng/mL at study start, or >250ng/mL during follow-up labs.
14. Are unwilling to provide blood samples during quarterly blood tests.
15. Are unwilling to take daily vitamin D.

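### Exclusion criterion 8 caps participants' own vitamin D at 1,000 IU/day and the consent procedure at 2,000 IU/day, so the stated 5,000 IU/day maximum does not hold

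*Combined protocol and SAP*

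**What the plan says.** **Section VIII, exclusion criterion 8.** The criterion applies to people who "Report already taking more than 400 IU of vitamin D daily as recommended by their health care provider". In deciding who is caught, it leaves some products out: "excluding multivitamins and excluding supplements that include vitamin D and calcium together". Such people may join if the prescriber agrees, and then "no more than 1,000 IU vitamin D may be taken daily in addition to the study medication". They are limited to the low-versus-moderate comparison, "producing a maximum dose of 5,000 IU per day". The criterion then defends that figure at some length, on the basis of "the combination of our 4,000 IU supplements and the patient's original supplement of up to 1,000 IU".

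**Section XIV, consent procedure.** This rule covers any supplement or supplements. For people whose products contain "2,000IU or less of vitamin D in total, they may continue to take those supplements while part of the study", the only condition is enrolment in the 400 versus 4,000 IU randomization; prescriber permission is not mentioned. For people taking more, "we will ask the subject to discontinue supplements in excess of 2,000IU during their time on the study supplement". That sentence does not mention the randomization.

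Both sections are current operative text, and neither refers to the other.

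**The concern.** Two sections that staff apply to the same applicant give different limits on the same quantity, vitamin D taken besides study drug. Criterion 8 turns its limit into a stated maximum daily dose and argues for that number. The consent procedure allows twice as much own intake, so anyone who relies on 5,000 IU/day as the upper bound for supplement users is relying on a figure that the consent rule does not deliver.

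There is also a practical consequence. Without a common rule, the limit an applicant gets may depend on which section the coordinator follows, and may differ between coordinators or sites. Own intake would then vary in a way that the protocol neither intends nor describes.

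**Working it through.** **Inputs.** Study doses of 400 and 4,000 IU/day for the low-versus-moderate comparison (Sections III and VII); own-intake cap of 1,000 IU/day (Section VIII, criterion 8); own-intake cap of 2,000 IU in total (Section XIV); stated maximum of 5,000 IU/day (criterion 8).

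**1. The plan's own figure.** Maximum = study dose + cap = 4,000 + 1,000 = 5,000 IU/day. This reproduces criterion 8 exactly, so the stated maximum depends on the 1,000 IU cap.

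**2. The same sum with the consent cap.** 4,000 + 2,000 = 6,000 IU/day. The excess is 6,000 − 5,000 = 1,000 IU/day, and 1,000 / 5,000 = 20%.

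**3. The two rules by band of provider-recommended intake** (a single product that criterion 8 counts):

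| Intake, IU/day | Criterion 8 | Consent procedure | Compatible? |
|---|---|---|---|
| Up to 400 | Not caught | May continue; 400 vs 4,000 only | Yes |
| 401–1,000 | Needs prescriber permission; low vs moderate | May continue; 400 vs 4,000 only; permission not mentioned | On the amount, yes; on permission, unclear |
| 1,001–2,000 | Over the cap, even with permission | May continue; 400 vs 4,000 only | No |
| Above 2,000 | Over the cap | Give up the excess above 2,000; randomization not stated | No, if the remainder is still above 1,000 |

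**4. Contrast between arms for a supplement user at the full cap.** With own intake *s*, the ratio is (4,000 + *s*) / (400 + *s*) and the difference is (4,000 + *s*) − (400 + *s*) = 3,600.

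| Own intake *s* | Low arm | Moderate arm | Ratio | Difference |
|---|---|---|---|---|
| 0 | 400 | 4,000 | 10.0 | 3,600 |
| 1,000 (criterion 8) | 1,400 | 5,000 | 3.6 | 3,600 |
| 2,000 (consent text) | 2,400 | 6,000 | 2.5 | 3,600 |

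Most of the fall in the ratio, from 10.0 to 3.6, already occurs under criterion 8. The discrepancy between the sections adds only the step from 3.6 to 2.5. The absolute difference does not change.

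**The case against.** The strongest reply is that the two rules measure different things. Criterion 8 concerns provider-recommended vitamin D and sets aside multivitamins and vitamin D/calcium products; the consent rule counts all supplements together. Eligibility screening comes before eConsent (Section XVII and Appendix A), so the consent rule could be read as addressing people who have already passed criterion 8. Staff could then apply both: provider-recommended vitamin D up to 1,000 IU, everything together up to 2,000 IU.

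This has some force. It may explain why two figures exist, and it confines the strict conflict to people on a provider-recommended 1,001 to 2,000 IU/day, including those who cut down to that range. But the documents do not state this reading, and it does not rescue the 5,000 IU/day figure, because a total of 2,000 IU of own intake still gives 6,000 IU/day. If the scopes are instead wholly separate, 5,000 IU/day survives for the criterion 8 group. People without a prescriber's involvement would then have the larger allowance, which sits oddly with criterion 8's argument about doses taken without medical supervision.

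A reader might also infer that the trial's safety case as a whole fails. The documents do not support that. The 5,000 IU/day figure is the maximum for the criterion 8 subgroup. The general case in Section III (Safety for higher dosing) refers to doses up to 10,000 IU/d with laboratory monitoring, and Section XI adds calcium checks at each draw.

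A reader might further infer that people who cut down to 2,000 IU may enter the low-versus-high comparison. Section XIV does not permit this; it is silent. Someone who has cut down arguably falls under the preceding sentence, with its limit to 400 versus 4,000 IU. One added clause would settle it.

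**Conclusion.** The inconsistency is real and should be corrected. As written, the stated 5,000 IU/day maximum holds only with the 1,000 IU cap; the consent procedure allows up to 6,000 IU/day in the 4,000 IU arm. The 6,000 figure assumes a participant who takes the full study dose and uses the whole consent allowance.

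A tempting further step is to say that the discrepancy blurs the low-dose control. The documents do not support this as a main finding. Own intake is allowed equally in both randomized arms, so the likely effect is dilution of the relative contrast rather than bias. The contradiction accounts for the smaller part of the fall in the ratio, and the absolute difference stays at 3,600 IU/day. The share of supplement users is not given, so the effect on power cannot be computed.

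Nor can the serum levels that Section III reports for 2,000 and 4,000 IU/d be used to show a shrunken contrast, because the intakes at the consent cap would be 2,400 and 6,000 IU/day.

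**What to change.** The sponsor and its clinical committee should:

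- reconcile criterion 8 in Section VIII with both supplement rules in Section XIV, so that one limit applies;
- state the scope of that limit: which products count towards it, including multivitamins and vitamin D/calcium combinations, and whether prescriber permission is needed;
- restate the maximum daily intake so that it follows from the limit;
- say which randomization applies to people who cut down to the limit;
- carry the same wording into the consent forms if they repeat the rule (they are not in the copy reviewed).

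Which limit is right is a clinical decision and is left to them. The cost is a wording amendment.

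Optional and secondary: tabulate own supplement intake by arm and add one sensitivity analysis by baseline supplement use. The surveys in Section III already collect supplements with doses at intake and changes at follow-up. Section IX adjusts for baseline vitamin D level and leaves its covariate list open, but does not name supplement use. This needs no new data, only one table and one analysis.

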### Summary of Consent Form Versions

**For those consented March 31 2022-December 31, 2022:** We will use consent form Version 10 (UCMC) or Version 11 (Ingalls), both in English and Spanish. This is because these consent forms are written for those who participate in the study for 6-9 months. Subjects who consent before October 1, 2022 will be in the study for 9 months. Subjects who consent on or after October 1, 2022 will be in the study for 6 months. This information is also clarified in these consent forms and in Table 3 of Section IV above. Version 10, like Version 8, has language for opt-in labs while Version 11 does not. We will use consent form Version 4 for Rush subjects.

For those who consented using UCM Consent Version 8 or 9, or Rush Consent Version 3 (thus who consented on or after January 1, 2022 and in follow up for less than 6 months), we wish to allow for the option to re-consent these subjects on UCM Consent Version 10 or 11, or Rush Consent Version 4, to allow these subjects to participate in the study for a full 9-month period (and would thus receive 4 total blood tests and 4 follow-up

surveys). This re-consent is entirely voluntary. If these subjects do not wish to re-consent, they will end their time in the study June 30, 2022.

**For those consented January 2023-March 31, 2023:** We will use consent form Version 12 (UCMC) or Version 13 (Ingalls), both in English and Spanish. With the removal of the final PTH lab approved in Amendment 54, we will then use consent form Version 14 (UCMA) or Version 15 (Ingalls), both in English and Spanish. This is because these consent forms are written for those who participate in the study for less than 6 months. This information is also clarified in these consent forms and in Table 4 of Section IV above. Version 12 and 14, like Versions 8 and 10, have language for opt-in labs while Version 13 and 15 do not.

## XV. Procedures to maintaining confidentiality

Electronic study data will be maintained on password-protected, encrypted devices in locked offices at UCM and RUMC, including internally using the standard of minimum necessary PHI, assigning subject IDs to each subject and using that as the mode of identification rather than name and/or MRN. All study staff will have up-to-date HIPAA training. Consent forms will be stored in HIPPA-compliant lab share drives maintained by the UCM Center for Research Informatics. Paper forms as related to the study will be stored in locked filing cabinets at UCM and RUMC in the site PI's office suites.

## XVII. Description of recruiting methods:

Given the current risk of COVID-19, we will use virtual recruiting as much as possible. We will recruit using a variety of mechanisms, including emails, flyers, presentations, and social media posts.

We plan to recruit at UCMC and Ingalls Memorial, and at Rush University near west side, South Loop and Oak Park locations.

*For employee recruitment:* We will begin by sending emails to all eligible employees via existing institutional listservs using the Employee Listerv email scripts and by engaging leaders in varying units to seek permission to present at meetings of their units, which typically now occur virtually by Zoom. While we will recruit in diverse settings across both sites, we will prioritize recruitment of health care workers in outpatient ambulatory

settings given the higher likelihood of exposure to outpatients and given greater COVID-19 testing of inpatients. At both sites we will prioritize front line clinicians, research and other staff (e.g., clinical research coordinators, cafeteria and custodial workers) with the greatest likelihood of exposure based on contact with patients or other colleagues. We expect these criteria to result in a population that significantly over represents African American persons, addressing a high-risk population since African Americans and HCWs are at increased risk of COVID-19, increasing our statistical power. Our outreach efforts will also prioritize participants who are older, where infection risk and adverse outcomes are more likely. As vaccines are rolled out to healthcare workers, we will also prioritize those less likely to have access to the vaccine right away.

*For community recruitment:* We will begin by leveraging our existing relationships with individuals already enrolled in the study and those in our broader UCM and Rush communities.

- For individuals newly enrolled in the study, we will send them a welcome email using either "Welcome and Share Email" scripts to ask them to share with their networks information about the study just after they consent to the study.
- For individuals who have been enrolled in the study for more than one month, we will reach out to them individually via email using the Existing Subject email scripts to inform them that in light of vaccine prioritization to HCWs, we are expanding our recruitment to adults in Chicagoland communities to give them access to the possible of benefits of COVID-19 prevention with vitamin D. We will ask them if they would be willing to forward the FAQ sheet to their family members, friends, or others in their network who they think may be interested.
- For groups of HCWs who we have reached already with recruitment materials, we will follow up with those groups using the Community Listserv scripts and inform them that in light of vaccine prioritization to HCWs, we are expanding our recruitment to adults in Chicagoland communities to give them access to the possible of benefits of COVID-19 prevention with vitamin D. We will re-attach the FAQ sheet and ask them to forward it to those in their networks who they think might be interested in participating.
- For HCWs who we have not yet reached out to about participating in the study, we will use the Community listserv scripts to both ask them if they are interested and ask if they could share the information with those who may be interested in their networks.
- For individuals who have previously been disqualified at enrollment due to ever having a self-reported positive PCR test or a positive baseline antibody test, we will contact these individuals and ask if they are interested in enrolling. We will have these individuals enroll using the same processes for new subjects.

For community recruitment other than HCWs and the social networks of study participants, we will begin by leveraging existing community relationships to reach out to primary contacts at a variety of community organizations via phone or email. We will also recruit in Chicagoland neighborhoods, handing out brochures and/or flyers to local businesses.

For community recruitment, we use the "Joint Interest Form- RedCap" on iPads or laptops when we are recruiting. RCs, RAs and Americorps members, when a potential participant indicates interest in learning more about the study, will enter potential participant information into this form so they can be later followed up with by study teams. This will allow the study team to answer questions and, as applicable, conduct screening, in a private setting at a time convenient for the potential participant.

We will ask relevant community organizations' leaders to disseminate study flyers, FAQ sheets, and listserv announcements to their organization and will seek permission to present at meetings. We will allow community organization leaders to decide what is the most appropriate mechanism to reach out their group, and we will provide them with the relevant recruitment materials accordingly. We will also leverage existing community relationships to recruit using social media. These include study staff tweeting recruitment announcements about the study and asking for help in re-tweeting the message, and our group providing social media posts to organizations to post themselves via Twitter, Instagram (via InstaStory or on the feed), Snapchat, Facebook (via Story or their wall), or NextDoor.

We will run also paid advertising campaigns on Facebook and Instagram. The Harris School of Public Policy social media team will manage these campaigns, and ads will be posted from the Harris social media accounts. We will target the ads to people over age 18 in the Chicago area who have broad Chicago-related interests, such as Chicago Public Schools or the White Sox. This targeting will increase effectiveness and efficiency of the ad campaign.

We will also be using a recruitment website, for which we provide the text (see Vitamin D joint study text). This website will recruit for both this study and for protocol 20-0847 (same PI) due to their overlapping study populations and overlapping study interventions and instruments. If participants are interested in this study (study option 2), they will be taken to a RedCap form (see RedCap form text) where they will provide contact information.

Below we provide a list of specific community organizations that we plan to reach out to for recruitment. We will update this list with new organizations in an amendment as we identify them.

- The University of Chicago community listservs
- Rush University community listservs
- Stroger Hospital of Cook County
- Friend Family Health
- Howard Brown Health
- Oak Street Health
- Bain & Company
- Ernst & Young
- PWC
- Polsinelli
- Sidley Austin LLP
- Winston Straun LLP
- The Chicago White Sox
- The Chicago Bulls
- Abbott
- McDonald's Corporation
- Chicago Fire Department
- Chicago Police Department
- The Chicago Sun-Times
- Chicago Defender
- Chicago Tribune
- Jewel-Osco
- Mariano's
- Walgreens
- CVS
- Trader Joe's
- Whole Foods
- Uber
- Lyft
- The City of Chicago
- Local area congregations
- Chicago Housing Authority
- Subway
- Jimmy John's
- Chicago Athletic Clubs

- LA Fitness
- Fitness Formula Clubs
- Orange Theory
- Core Power Yoga
- Altura

Interested subjects will be directed to a recruitment line staffed by our research staff or, if recruited from an in-person setting, will complete the Joint Study Interest form in RedCap and be contacted by research staff at a later time to review the study and eligibility requirements in a private setting. Once potential subjects are screened for eligibility and express interest in the Intake Form in RedCap, we use the methods described below in Appendix A. We will send them a RedCap eConsent form via text or email, depending on preference, and telephone them to walk them through the informed consent process. Our research team has already developed and successfully implemented protocols for virtual recruitment and consent for other studies using RedCap eConsent in which consent forms are either texted or emailed to all signors and signed digitally. We will also operate a telephone line staffed by our research staff on which potential participants can have questions answered and assistance with assessing eligibility. They can then either complete electronic consent via RedCap eConsent or have a paper consent form prepared for them to sign physically, which will be dropped off at a location convenient for the subject by a CRC. We will not exclude potential participants currently working virtually because we expect this to change for many workers over the study period. Study recruitment will take place through March 31, 2022, or, if we receive a second no-cost extension in Spring 2022, through March 31, 2023 (see above timelines). For HCW recruitment, though our primary recruitment approaches will be virtual, the research team will also hang posters throughout UCM/Ingalls campuses and Rush University, including showing these posters electronically with approval from UCM/Rush marketing teams in areas with screens providing employee announcements, and place flyers in departmental mailboxes. For community recruitment, we will similarly follow primarily virtual recruitment approaches and distribute flyers for dissemination at the physical location as appropriate.

To maximize retention rates, our CRCs and study staff will monitor completed drop-in laboratory visits according to the 3-month schedule and follow-up with subjects via telephone and email reminders at each wave to each subject until the lab visit is completed. CRCs and analysts will also monitor survey completion at each wave and send out email and telephone reminders to subjects who have not completed the survey. Laboratory visits will occur for all tests at the same time during study sites' laboratory hours to minimize inconvenience to subjects.

